3.3.1.2 Dose reductions (Summarized in Table 11)

If any non-hematologic AE observed was grade 3 (except nausea and vomiting) and/or if platelets $< 50 \times 10^9/L$ and/or ANC $< 1 \times 10^9/L$, then the dose should be reduced by one dose level. For patients who would require dose reductions to a dose level < -2 as defined in table 10, temozolomide will be stopped. Also, if any of the same non-hematologic grade 3 AE recurs (except, nausea and vomiting,) after reduction for that AE, then temozolomide will be stopped.

If any treatment-related non-hematologic AE observed was grade 4 (except nausea and vomiting) then adjuvant temozolomide treatment should be stopped.

Any dose reductions of temozolomide will be determined according to (1) non-hematologic AE, as well as (2) the lowest/worst ANC and platelet counts observed. No dose escalation should be attempted. If the dose reduction occurs in the middle of the cycle, the reduced dose should be applied as soon as the treatment resumes (i.e. next dose).

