Patients will be enrolled to Arm 1 only to receive Zotiraciclib (at Dose level 0 and in combination of dd TMZ). TG02 dose is 200 mg/day orally on days 1, 12, 15, and 26 on a 28-days cycle, except for that the first dose of Zotiraciclib (TG02) will be given 3 days prior to Day1 in cycle 1. TMZ is administered at 125mg/m² daily on days 1-7 and 15-21 orally on a 28-days cycle.

3.2.2 Phase II treatment:

The combination treatment selected from phase I (with better PFS4) will be tested against the TMZ alone with the same dosing schedule as it is in the combination arm. Patients will be randomized on a 1:1 basis between two competing treatment arms: TMZ + Zotiraciclib (TG02) versus TMZ alone using a Bayesian phase II trial design. The details of the design are provided in Section 8.

The dosage for the combination arm is derived from the MTD of the combination determined in the phase I component of the study. The treatment schedule will be identical to that described above in the phase I component, with each cycle comprising 28 days.

Patients will continue treatment until tumor progression or unacceptable toxicity occurs or completion of 12 cycles of treatment. At progression, patients randomized to the control arm (TMZ alone) will be offered the opportunity to continue TMZ and the additional treatment with Zotiraciclib (TG02). After administration of 12 cycles of treatment, patients may stay on the study treatment, if there is evidence of clinical benefit based on treating physician's discretion.

If patient vomits Zotiraciclib (TG02), do not re-administer.

3.3 DOSE MODIFICATION/DELAYS:

If an adverse event occurs wherein both TMZ and Zotiraciclib (TG02) would require dose de-escalation, the Principal Investigator shall have the discretion of first dose reducing one of the 2 study drugs with the consideration of previously known drug toxicities/side effects in an effort to further define attribution.

Table 8: Start of Each Cycle for both TMZ and Zotiraciclib (TG02)		
Temozolomide and Zotiraciclib (TG02)		
Hematologic*	ANC $\geq 1.5 \times 10^9/L$ and PLT $\geq 100 \times 10^9/L$	No dose modification
	ANC $< 1.5 \times 10^9/L$ and/or Platelet count $< 100 \times 10^9/L$	Delay up to 4 weeks until ANC $\geq 1.5 \times 10^9/L$ and PLT $\geq 100 \times 10^9/L$. If unresolved after 4 weeks, then stop. If resolved, dose delay/reductions based on Table 9.
Non-Hematologic	Grade 1 or less	No dose modification

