	Grade 2	Zotiraciclib (TG02): Delay up to 4 weeks until \leq Grade 1. If unresolved after 4 weeks, then dose reduce by 1 dose level. Temozolomide: dose delay/reductions based on Table 9, if adverse event attributed to Temozolomide.
	Grade 3	Zotiraciclib (TG02): Delay up to 4 weeks until \leq Grade 1. If unresolved after 4 weeks, then stop. If resolved to \leq Grade 1, then dose reduce by 1 dose level. Temozolomide: dose delay/reductions based on Table 9, if adverse event attributed to Temozolomide.
	Grade 4	Discontinue treatment

*With the exception of lymphopenia, grade 1-4. Patient may start a cycle with G2 WBC, as long as the ANC $\geq 1.5 \times 10^9/L$.

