3.3.1.1 Delay

For treatment on day 1 of each cycle (within the prior 72 hours), ANC $\geq 1.5 \times 10^9/L$, platelet count $\geq 100 \times 10^9/L$ and all grade 2 -3 non-hematologic AEs (except nausea and vomiting) must have resolved (to grade ≤ 1). For grade 4, discontinue treatment. For the purposes of this study, any clinically insignificant Grade 2 or 3 electrolyte abnormalities with attribution of unlikely related to or unrelated to study medications, will not require holding or dose-reducing study medications.

If AEs persist, treatment may be delayed by 1 week for up to 4 consecutive weeks. If, after 4 weeks of delay, all AEs have still not resolved to grade 1 or less: then any further treatment with temozolomide should be stopped, as summarized in Table 8 and Table 11.

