Table 10: Zotiraciclib (TG 02) Dose Modification Table	
Dose Level	TG 02 (mg/day on days 1, 12, 15, 26 per 28 day cycle)*
-1	150
0	200
1	250
2	300

Summary of Dose Modification or Discontinuation

Table 11: Dose Modifications and Delay*				
	Zotiraciclib (TG02)		TMZ	
Grade	Hematologic**	Non-hematologic	Hematologic**	Non-hematologic
0-1	No dose modification	No dose modification	No dose modification	No dose modification

Table 11: Dose Modifications and Delay*				
	Zotiraciclib (TG02)		TMZ	
2	Hold until resolved to ≤ G1; if persists beyond 4 weeks, dose reduce one level.	Hold until resolved to ≤ grade 1; if > 4 weeks then dose reduce 1 level.	Hold until resolved to ≤ grade 1; if > 4 weeks then dose reduce 1 level.	No dose modifications for non-hematologic AEs (G 0-2), unless the adverse event attributed to Temozolomide.
3	If not recovered to ≤ G2 within 3 days, STOP. If recovered to ≤ G2 within 3 days, re-start @ one dose level lower once recovered to G1 or less.***	Delay up to 4 weeks until ≤ Grade 1. If unresolved after 4 weeks, then stop. If resolved to ≤ grade 1; then dose reduce by 1 level.	Hold until resolved to ≤ grade 1; if > 4 weeks, then stop.	Hold until resolved to ≤ grade 2; if greater than 4 weeks then stop. If less than 4 weeks, reduce by one dose level. If the same non-hematologic grade 3 AE recurs after reduction for that AE, then stop.
4	If not recovered to ≤ G2 within 3 days, STOP. If recovered to ≤ G2 within 3 days, re-start @ one dose level lower once recovered to G1 or less	Stop treatment.	Stop treatment.	Stop treatment.

* If the patient develops a lower extremity deep venous thrombosis and requires anticoagulation or intervention (grade 2 or 3 toxicity), treatment may be restarted after a 2-week rest period if the patient is stably anticoagulated and is judged medically stable to begin chemotherapy. (Please note: DVT is graded in the CTC version 4.0 as grade 1= superficial thrombosis, grade 2= DVT, medical intervention indicated, grade 3= uncomplicated pulmonary embolism, medical intervention indicated, grade 4=life-threatening pulmonary embolism, cerebrovascular event, arterial insufficiency, urgent intervention indicated).

** With the exception of lymphopenia, grade 1-4.

***If G3 neutropenia recovers within 72 hours, the Principal Investigator may consider no dose reduction of Zotiraciclib (TG02).

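### For a grade 4 neutrophil or platelet count that recovers within 4 weeks, section 3.3.1.2 lowers temozolomide one level but Table 11, its named summary, stops it; grade 2 counts lasting over 4 weeks are also handled inconsistently

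*Combined protocol and SAP*

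**What the plan says.** Four places govern temozolomide after low counts.

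- **Section 3.3.1.2**: for platelets below 50 and/or ANC below 1 x10^9/L, "then the dose should be reduced by one dose level". Reductions follow the worst count seen. Its grade 4 stop is narrower: "If any treatment-related non-hematologic AE observed was grade 4 (except nausea and vomiting) then adjuvant temozolomide treatment should be stopped". A patient who would need to go below level -2 stops.
- **Table 11** (under 3.3.2, but named in the 3.3.1.2 heading as that section's summary): temozolomide, hematologic, grade 4: "Stop treatment". Grade 3: hold, and stop if the hold passes 4 weeks. Grade 2: hold, and reduce one level if the hold passes 4 weeks.
- **Table 8** (section 3.3, start of each cycle): for ANC below 1.5 or platelets below 100, whatever the grade, delay up to 4 weeks. "If unresolved after 4 weeks, then stop. If resolved, dose delay/reductions based on Table 9". Its grade 4 entry, "Discontinue treatment", sits in the non-hematologic block.
- **Section 3.3.1.1**: after a sentence listing ANC, platelets and non-hematologic events, it says "For grade 4, discontinue treatment". After 4 weeks of delay without resolution, temozolomide is stopped, and Tables 8 and 11 are both cited for this.

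Section 3.3.1 assigns Table 11 to events during a cycle and Table 8 to the start of a cycle. Section 3.10.1 separately removes a patient from protocol therapy when treatment-related adverse events do not resolve within a 4-week rest.

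**The concern.** A summary table should repeat the rule that it summarises. Here the text and its own summary give different actions for the same laboratory result, and the protocol has no precedence clause. Two investigators could follow the protocol faithfully and treat the same patient in opposite ways.

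The event is foreseeable. Section 1.2.7 describes a grade 4 neutropenia within 24 hours of one zotiraciclib dose that was back to grade 1 a day later. It also says that hematologic toxicity in this trial has mainly been attributed to temozolomide. Section 3.3.2 expects prolonged myelotoxicity to be attributed to temozolomide and sends it to the 3.3.1 rules. In the Phase II control arm temozolomide is the only study drug, so stopping it ends treatment on that arm. At stake are the treatment and safety handling of individual patients.

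**Working it through.** The plan gives no figure to reproduce, so the check sets the rules side by side on worked cases and then sizes the exposure.

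**1. Do grade 4 counts fall inside the 3.3.1.2 reduction range?** The grade 4 cuts printed in 13.1.5 are ANC below 500 cells/µL (0.5 x10^9/L) and platelets below 20,000/µL (20 x10^9/L). Both lie inside ANC <1 and platelets <50. Yes.

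**2. Grade 4 case: temozolomide at level 0, ANC nadir 0.4 x10^9/L, recovered within 4 weeks.**

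| Text | Action |
|---|---|
| 3.3.1.2 | Reduce one level: 125 to 100 (dose-dense) or 50 to 40 mg/m2 (metronomic) |
| Table 8, hematologic row | No stop; treatment may go on after recovery |
| Table 11 | Stop |
| 3.3.1.1, grade 4 sentence | Stop if it covers counts; silent if it covers only non-hematologic events |

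The dose step from Table 9 is 100/125 = 40/50 = 0.80. From level -1 it is 80/100 = 32/40 = 0.80.

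**3. Where do the texts not differ?** If the count is unresolved after 4 weeks of delay, 3.3.1.1 and Table 8 stop temozolomide. If the patient is already at level -2, 3.3.1.2 stops it too. The conflict is confined to counts that recover within 4 weeks in patients at level 0 or -1.

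**4. Grade 2 counts lasting over 4 weeks.** Table 11 reduces one level. Section 3.10.1 removes the patient if a treatment-related adverse event is unresolved after a 4-week rest. Section 3.3.1 treats the triggers for dose modification as adverse events, so counts come under 3.10.1 when they are treatment-related.

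Section 3.3.1.1 and Table 8 also stop temozolomide, but they count delay of the new cycle. Suppose that clock starts at the planned day 1 (day 29 of the current cycle). A hold from day *d* must then last more than 57 - *d* days to reach their stop. From day 14 that is 57 - 14 = 43 days. A 35-day hold from day 14 ends on day 49, only 49 - 29 = 20 days into the delay. Table 11 then says reduce, Table 8 allows resumption, and only 3.10.1 says remove. Past 43 days, 3.3.1.1 and Table 8 say stop as well.

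**5. Exposure.** Section 13.1.5 gives first-cycle grade 4 neutropenia in the pooled temozolomide database as 4/61 (over age 70) and 62/871 (70 or under):

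(4 + 62)/(61 + 871) = 66/932 = 0.0708

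- Phase II maximum (10.2): 80 x 0.0708 = 5.7 expected; binomial 95% range 2 to 11.
- Added Phase I patients (10.1): 12 x 0.0708 = 0.85 expected; chance of at least one = 1 - 0.9292^12 = 0.59.
- Grade 4 thrombocytopenia: (6 + 48)/(63 + 879) = 54/942 = 0.0573; 80 x 0.0573 = 4.6 expected; range 1 to 9. Some of these patients may also be among the neutropenia cases.

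**The case against.** **Table 11 may be taken to settle grade 4.** It is the explicit grade-by-grade table, it gives the more cautious action, and the grade 4 sentence in 3.3.1.1 may agree with it. The team also discusses each patient (7.4.1). This is a good reason to make the Table 11 stop the default. It does not remove the conflict. If the 3.3.1.1 sentence covers counts, it contradicts 3.3.1.2; if it does not, it gives Table 11 no support. Case discussion does not say which rule the protocol prescribes.

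**The tables have different scopes.** This is true of Tables 8 and 11, but it cannot reconcile 3.3.1.2 with the table named as its own summary. The scope argument does carry weight for grade 2. A reader might infer that any hold over 28 days passes the next day 1 and so meets the Table 8 stop. The documents do not support that, because the Table 8 and 3.3.1.1 clock runs on delay of the new cycle. The direct contradiction for such a hold is with 3.10.1. The citation of Table 11 in 3.3.1.1 fits its grade 3 cell, not its grade 2 cell.

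**Table 8 does contain a stop.** Correct: it stops temozolomide when counts are unresolved after 4 weeks. What it lacks is a stop triggered by a grade 4 count.

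**The counts overstate the effect.** This stands. They are expected numbers with a grade 4 count, not numbers treated differently.

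**Conclusion.** The concern holds. For a grade 4 ANC or platelet count that recovers within 4 weeks in a patient above level -2, one text reduces temozolomide by 20% and its named summary stops it. Nothing in the protocol resolves this. For grade 2 counts lasting over 4 weeks, the Table 11 cell conflicts with 3.10.1, and with 3.3.1.1 and Table 8 once a new cycle has been delayed 4 weeks.

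The size is illustrative: about 6 of 80 Phase II patients and about 1 of the 12 added Phase I patients with grade 4 neutropenia in cycle 1. This assumes that the label's pooled rate carries over to these schedules. The number whose treatment differs is smaller, because patients who do not recover within 4 weeks stop under either text. Later cycles and any zotiraciclib effect are not counted. The contradiction itself depends on none of these figures.

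Two stronger readings are not supported:

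- **Dosing through grade 4.** Section 3.3.1.1 sets recovery thresholds (ANC at least 1.5, platelets at least 100 x10^9/L) "For treatment on day 1 of each cycle (within the prior 72 hours"), and for a mid-cycle reduction "the reduced dose should be applied as soon as the treatment resumes (i.e. next dose"). The question is stop versus resume.
- **Distorted DLT counts or a biased randomised comparison.** Section 3.1.3 treats a cycle 1 reduction, hold or discontinuation alike as a DLT at the investigator's discretion. PFS in 6.3.8 runs to progression or death whatever the treatment. The documents give no basis for claiming an effect on either.

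**What to change.** 1. **Grade 4 counts.** State one temozolomide rule in 3.3.1.1, 3.3.1.2, Table 8 and Table 11. The default is to keep the Table 11 stop: limit the 3.3.1.2 reduction to grade 3 counts, add a grade 4 stop to the Table 8 hematologic row, and say that the 3.3.1.1 sentence covers counts. If the sponsor prefers to resume, change the Table 11 cell to hold and then resume one level lower after recovery, and limit the 3.3.1.1 sentence to non-hematologic events.
2. **Grade 2 counts over 4 weeks.** Change the Table 11 temozolomide cell to stop if unresolved after 4 weeks, in line with 3.3.1.1, Table 8 and 3.10.1. If reduction is preferred, amend all three, including 3.10.1. Either way, say when the 4-week clock starts.
3. **Minor edits in the same revision.** Add the one-level reduction required by 3.3.1.2 to the Table 11 temozolomide grade 3 hematologic cell, which gives no dose on resuming. In 3.3.1.2, correct the reference to Table 10 (zotiraciclib doses, with no level -2) to Table 9.

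The cost is wording in two sections, one row of Table 8 and two or three cells of Table 11, plus 3.10.1 if reduction is chosen in item 2. Sample size, visits and analysis do not change.

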3.3.2 Zotiraciclib (TG02) Dose Modifications

If multiple AEs are seen, the dose administered should be based on the dose reduction required for the most severe grade of any single AE. Prior studies of Zotiraciclib (TG02) indicate that non-hematologic toxicities have been the dose-limiting toxicities. Therefore, in the combination regimens, attribution of treatment-related toxicities will be made based on best available information. As Zotiraciclib (TG02) has not been reported with high rates of prolonged myelotoxicity, these toxicities will likely be attributed to temozolomide and dose modifications

made as outlined in Section 3.3.1 above. Conversely, non-hematologic adverse events such as nausea and vomiting, intractable diarrhea, fatigue and prolongation of the QTc interval on ECG will be attributed to Zotiraciclib (TG02). Liver toxicities are a known toxicity of TMZ, which has been tested extensively in patients with high grade glioma. Zotiraciclib (TG02) has also been reported to cause elevated liver enzymes. To better understand the attribution of this toxicity, in the event of elevated ALT/ AST of grade 2 or above when a patient has received the combined treatment, dose modification will be made on one drug at a time. Should the need for dose modification arise again due to the same toxicity, dose of the second drug will be reduced. If a dose reduction occurs in the middle of the cycle, the reduced dose should be applied as soon as the treatment resumes.

Details for dose modification, delay at beginning of each cycle and during the cycle are summarized in Table 8 and Table 11 respectively.

The dose of Zotiraciclib (TG02) will be initiated at the phase I dose for patients enrolled on the dose-finding component or at the MTD for both the cohort expansion of the phase I and the phase II component of the trial. The same dose will be continued unless \geq grade 3 drug related toxicity occurs; treatment will be held until toxicity resolves to grade 1 or less. At that time, the dose will be reduced to one level below the dose that caused the grade 3 toxicity. Only two dose reductions will be allowed for Zotiraciclib (TG02). Patients enrolled prior to determination of the MTD will have stepwise reductions as necessary based on the Table 10 below. Please note, if the MTD is 150 mg/day, then no dose reduction will be allowed. Additionally, if the patient is treated at dose Level 0, only one dose reduction (to 150 mg/day) will be allowed.

Table 10: Zotiraciclib (TG 02) Dose Modification Table	
Dose Level	TG 02 (mg/day on days 1, 12, 15, 26 per 28 day cycle)*
-1	150
0	200
1	250
2	300

Summary of Dose Modification or Discontinuation

Table 11: Dose Modifications and Delay*				
	Zotiraciclib (TG02)		TMZ	
Grade	Hematologic**	Non-hematologic	Hematologic**	Non-hematologic
0-1	No dose modification	No dose modification	No dose modification	No dose modification

Table 11: Dose Modifications and Delay*				
	Zotiraciclib (TG02)		TMZ	
2	Hold until resolved to ≤ G1; if persists beyond 4 weeks, dose reduce one level.	Hold until resolved to ≤ grade 1; if > 4 weeks then dose reduce 1 level.	Hold until resolved to ≤ grade 1; if > 4 weeks then dose reduce 1 level.	No dose modifications for non-hematologic AEs (G 0-2), unless the adverse event attributed to Temozolomide.
3	If not recovered to ≤ G2 within 3 days, STOP. If recovered to ≤ G2 within 3 days, re-start @ one dose level lower once recovered to G1 or less.***	Delay up to 4 weeks until ≤ Grade 1. If unresolved after 4 weeks, then stop. If resolved to ≤ grade 1; then dose reduce by 1 level.	Hold until resolved to ≤ grade 1; if > 4 weeks, then stop.	Hold until resolved to ≤ grade 2; if greater than 4 weeks then stop. If less than 4 weeks, reduce by one dose level. If the same non-hematologic grade 3 AE recurs after reduction for that AE, then stop.
4	If not recovered to ≤ G2 within 3 days, STOP. If recovered to ≤ G2 within 3 days, re-start @ one dose level lower once recovered to G1 or less	Stop treatment.	Stop treatment.	Stop treatment.

* If the patient develops a lower extremity deep venous thrombosis and requires anticoagulation or intervention (grade 2 or 3 toxicity), treatment may be restarted after a 2-week rest period if the patient is stably anticoagulated and is judged medically stable to begin chemotherapy. (Please note: DVT is graded in the CTC version 4.0 as grade 1= superficial thrombosis, grade 2= DVT, medical intervention indicated, grade 3= uncomplicated pulmonary embolism, medical intervention indicated, grade 4=life-threatening pulmonary embolism, cerebrovascular event, arterial insufficiency, urgent intervention indicated).

** With the exception of lymphopenia, grade 1-4.

***If G3 neutropenia recovers within 72 hours, the Principal Investigator may consider no dose reduction of Zotiraciclib (TG02).

If leukopenia is grade 2 or above while ANC is grade 1 or less, the principal investigator may not consider it for dose modification and delay.

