1.2.7 Rationale for pharmacokinetic, pharmacogenetic and neutrophil function assay

Since the clinical trial 17C0009 was open to accrual, an unexpected phenomenon has been observed on multiple occasions- neutropenia with quick onset and quick recovery. Per current protocol, the hematologic toxicities have been mainly attributed to TMZ which is known for the bone marrow toxicities, including thrombocytopenia, leukopenia, neutropenia and lymphopenia. The complete blood count (CBC) of more than one patient happened to be tested based on clinical needs at several occasions. In those tests, absolute neutrophil count (ANC) in some patients was found to be decreased significantly. Interestingly, the low ANC can be found to be recovered within 24-48 hours in most cases. In one case, patient was found to have grade 4 neutropenia within 24 hours after one dose Zotiraciclib (TG02) but recovered to grade 1 neutropenia 24 hours later. The quick onset and quick recovery suggested that the bone marrow dysfunction is unlikely to be the etiology for the neutropenia that was observed in these cases. In addition, in most cases where this transient neutropenia occurred, there were no decreases in lymphocytes, platelets and hemoglobin. Although there were no serious consequences, such as infection in these cases, study drug had to be discontinued. Without knowing the pathophysiology of this type of neutropenia, the study drug can be discontinued prematurely. On the other hand, patients will be at risk if the follow up lab tests are not scheduled appropriately. It would be important to understand the effect of Zotiraciclib (TG02) on neutrophil biology.

To analyze the neutrophil function after Zotiraciclib (TG02) administration, information from pharmacokinetic study is crucial. To further understand why this neutropenia only happened in a subgroup of patients but not all patients receiving Zotiraciclib (TG02), we will add pharmacogenetic study by analyzing the genomic DNA and assess genotype of the most relevant drug metabolizing enzymes and transporters (DMET).

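### For a brief grade 4 neutropenia after TG02, Table 11 stops temozolomide while Section 3.3.1.2 only reduces it, and Sections 3.3.2 and 1.2.7 leave attribution unreconciled

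*Combined protocol and SAP*

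**What the plan says.** **Attribution.** Section 3.3.2 sets a default: "As Zotiraciclib (TG02) has not been reported with high rates of prolonged myelotoxicity, these toxicities will likely be attributed to temozolomide", with dose changes under Section 3.3.1. It adds that "attribution of treatment-related toxicities will be made based on best available information". Section 1.2.7 records that under the protocol "the hematologic toxicities have been mainly attributed to TMZ", and then describes a different pattern in this trial. In one case a "patient was found to have grade 4 neutropenia within 24 hours after one dose Zotiraciclib (TG02) but recovered to grade 1 neutropenia 24 hours later". It comments: "The quick onset and quick recovery suggested that the bone marrow dysfunction is unlikely to be the etiology for the neutropenia". It also says that the pathophysiology is not known and that study drug may be stopped prematurely as a result.

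**Action on each drug.** Table 11 has one hematologic column for TG02 and another for TMZ. At grades 3 and 4 the TG02 column turns on a 3-day recovery: "If not recovered to ≤ G2 within 3 days, STOP"; otherwise TG02 restarts one level lower. A footnote lets the Principal Investigator waive the TG02 reduction for grade 3 neutropenia that recovers within 72 hours. The TMZ column says hold at grade 3, with a stop only beyond 4 weeks, and stop at grade 4. Section 3.3.1.2, whose title refers to Table 11 as its summary, lowers TMZ one level when the absolute neutrophil count (ANC) is below 1 × 10⁹/L and stops it only if a level below -2 would be needed.

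**Other provisions.** Section 3.3.1 permits TG02 to continue when TMZ is discontinued. Section 3.3 says that, when both drugs would need de-escalation, "the Principal Investigator shall have the discretion of first dose reducing one of the 2 study drugs".

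**The concern.** The plan recognises a neutropenia that follows TG02, yet keeps a default that looks to TMZ for blood-count toxicity, and its table and text disagree on what then happens to TMZ. Section 3.3.2 also rests on the statement that dose-limiting toxicities of TG02 have been non-hematologic. Section 1.2.2.2 lists neutropenia as one of the two dose-limiting toxicities in the carfilzomib combination, and reports moderate to severe neutropenia among the first 16 patients of this trial.

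Two things are at stake. First, two clinicians following the same protocol could take different actions for the same event. Second, Phase II is meant to isolate the effect of adding TG02 to TMZ. If a transient drop after TG02 leads to TMZ being stopped, some combination-arm patients would no longer be receiving the backbone to which TG02 was added.

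**Working it through.** No arithmetic in the plan underlies this point. The check follows one event at a time through the rules.

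**Step 1. Does Section 3.3.1.2 cover a grade 4 neutropenia?** Section 13.1.5 gives grade 4 as ANC below 500 cells/µL, which is 0.5 × 10⁹/L. That is below the 1 × 10⁹/L trigger, so it does.

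**Step 2. The rules side by side.**

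| Event | TG02, Table 11 | TMZ, Table 11 | TMZ, 3.3.1.2 |
|---|---|---|---|
| A. Grade 4, back to grade 1 within 3 days (the case in 1.2.7) | Restart one level lower | Stop | One level down |
| B. Grade 3, same recovery | Restart one level lower; waiver possible | Hold; stop only beyond 4 weeks | One level down if ANC < 1 × 10⁹/L |
| C. Grade 3 or 4, not at grade 2 or less within 3 days | Stop | Grade 3: as in B. Grade 4: stop | One level down if ANC < 1 × 10⁹/L |

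**Step 3. Event A.** Under Table 11, TMZ ends after one event. Because the table uses hold elsewhere for a temporary interruption, stop is read here as permanent. Under 3.3.1.2, Table 9 provides 125 → 100 → 80 mg/m² (dose-dense) or 50 → 40 → 32 mg/m² (metronomic). Two such reductions are available, so only a third event would stop TMZ. One event therefore gives two different outcomes for TMZ. With Section 3.3.1, the Table 11 outcome can leave the patient on TG02 alone.

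**Step 4. Event B.** A single transient grade 3 event does not remove TMZ under either rule. The problem of losing TMZ after one brief event is confined to grade 4.

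**Step 5. Event C.** The mismatch runs the other way. Table 11 stops TG02 for a slow recovery, while 3.3.2 regards prolonged myelotoxicity as likely due to TMZ.

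**Step 6. Is attribution a condition?** Section 3.3.2 ties the TG02 reduction to drug-related toxicity and has a one-drug-at-a-time rule for liver enzymes. Table 11 mentions attribution for grade 2 non-hematologic events under TMZ. Neither hematologic column does. Section 3.3.1.1 adds an instruction to discontinue at grade 4 without making clear whether it covers blood counts or only non-hematologic events.

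**Step 7. Could scheduled counts pick up such a drop?** TG02 is given on days 1, 12, 15 and 26. Blood counts are scheduled in weeks 2 and 4, and the day 1 count is taken within the prior 72 hours. Section 1.2.4 places day 26 exactly 3 days before the next day 1. Counts can therefore fall in the 24 to 48 hours in which 1.2.7 saw recovery, but need not. In cycle 1 the first TG02 dose comes 3 days before any on-study TMZ, so a drop in that interval cannot be due to on-study TMZ.

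**The case against.** The strongest reply is that the sentence in 3.3.2 does not itself remove TMZ. It leads to Section 3.3.1, where 3.3.1.2 reduces the dose, and Table 11 is only a summary. That is right about the sentence: the removal comes from the grade 4 TMZ cell. But the plan does not say that text prevails over table, and 3.3.1.1 and 3.3.1.2 both point to Table 11.

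A reader might infer that 3.3.2 and 1.2.7 flatly contradict each other, or that the plan attributes the neutropenia to TG02. The documents do not go that far. Section 3.3.2 is hedged and concerns prolonged toxicity. Section 1.2.7 concerns a transient drop, points towards TG02, and leaves the cause open. Section 1.2.2.2 gives no onset or recovery times.

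A reader might also take the discretion in Section 3.3 as a third competing rule. It is a tie-breaker for when both drugs would need de-escalation, and it does not expressly override an instruction to stop.

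The plan already handles part of the problem through the 3-day window for TG02, the grade 3 waiver, and repeat counts in Phase I. None of these reaches the grade 4 TMZ cell.

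Finally, PFS runs from registration to progression or death, and toxicity-driven dose changes are part of an assigned regimen's effect. This stands against any claim that the primary comparison is uninterpretable or biased in a known direction.

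**Conclusion.** The point holds as an unreconciled set of rules. For a brief grade 4 neutropenia after TG02, Table 11 and Section 3.3.1.2 give different actions on TMZ. For a slow recovery, Table 11 stops TG02, which sits badly with the attribution default in 3.3.2.

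The effect on Phase II depends on the Table 11 reading being applied, on a count being drawn during the drop, and on TG02 then being continued, which Section 3.3.1 permits but does not require. A drop following TG02 has no counterpart in the control arm before crossover. Under those conditions the add-on PFS contrast becomes harder to interpret; the documents support no stronger statement.

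It is tempting to put a number of lost TMZ courses on this. The documents give no rate of transient grade 4 neutropenia, and 1.2.7 describes one grade 4 case, so no number can be stated. For scale only, each affected patient would be 1/40 = 2.5% of a full combination arm.

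**What to change.** Reconcile Sections 1.2.7, 3.3, 3.3.1.1, 3.3.1.2, 3.3.2 and Table 11 so that one blood-count event leads to one action for each drug. State in Table 11 whether each hematologic column applies regardless of attribution or only to the drug to which the event is attributed. Make clear whether the grade 4 sentence in 3.3.1.1 covers blood counts. Correct the reference in 3.3.1.2 to Table 10, since the TMZ levels are in Table 9.

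For every grade 3-4 count, record the drug to which it was attributed and the time since the last TG02 dose, so that the frequency of the problem and its effect on TMZ exposure can be described by arm.

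Which action is right for either drug, and how attribution should be decided, are clinical decisions for the sponsor; nothing is proposed on them here. The cost is amendment wording and two case report form fields, with no extra visits. It should be done before Phase II.
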